12.2 Serious Adverse Events

SAEs will be collected from the time of informed consent and for the duration of the study. SAEs and AEs listed in the Sponsor's IB will be considered expected events. See the Sponsor **IB** for additional details of drug expected AEs.

12.2.1 Definition of Serious Adverse Event

An SAE is any event that meets any of the following criteria at any dose:

- results in death,
- is life-threatening,
- results in inpatient hospitalization or prolongation of existing hospitalization,
- results in persistent or significant disability/incapacity

- is a congenital anomaly/birth defect.
- Other: Important medical events that may not result in death, be life-threatening, or require hospitalization, may be considered an SAE when, based upon appropriate medical judgment, they may jeopardize the subject and may require medical or surgical intervention to prevent one of the outcomes listed in this definition.

Examples of such events are (but not limited to):

- Intensive treatment in an emergency room or at home for allergic bronchospasm
- Blood dyscrasias or convulsions that do not result in inpatient hospitalization
- Development of drug dependency or drug abuse
- Potential drug induced liver injury (see [Section 12.2.5](#))
- Abuse or overdose of medication
 - Potential study medication abuse (including cases of excessive non-compliance with study medication dosing instructions or subjects who discontinue treatment without returning study medication) should be documented in the source record and reported as an AE or SAE as appropriate. Investigators must monitor subjects for possible cases of abuse of study medication (subjects taking study drug for non-therapeutic purposes, e.g., for psychoactive effects such as high feeling or euphoria). Investigators should obtain more information and explanation from subjects when there are study drug accountability discrepancies.
 - Potential study medication overdose is defined in [Section 12.2.4](#).

In general, hospitalization signifies that the subject has been detained (usually involving at least an overnight stay) at the hospital or emergency ward for observation and/or treatment that would not have been appropriate in the physician's office or outpatient setting. When in doubt as to whether 'hospitalization' occurred or was necessary, the AE should be considered serious.

The following hospitalizations are not considered SAEs in Biohaven clinical studies (but may be considered non-serious AEs):

- A visit to the emergency room or other hospital department < 24 hours that does not result in an admission (unless considered "important medical event" or event that is life-threatening);
- Elective surgery planned prior to signing consent;
- Admissions as per protocol for a planned medical/surgical procedure;
- Routine health assessment requiring admission (i.e., routine colonoscopy);

- Admission encountered for another life circumstance that carries no bearing on health and requires no medical intervention (i.e., lack of housing, care-giver respite, family circumstances).

Disability/incapacitating: An AE is incapacitating or disabling if the experience results in a substantial and/or permanent disruption of the subject's ability to carry out normal life functions.

12.2.2 Collection and Reporting of Serious Adverse Events

Following the subject's written consent to participate in the study, all SAEs, whether related or not related to study drug, must be collected, including those thought to be associated with protocol-specific procedures. All SAEs must be collected at follow-up, up to 10 days after last dose treatment. The investigator should report any SAE occurring after this time period that is believed to be related to study drug or protocol-specific procedures.

All SAEs should be followed to resolution or stabilization.

An SAE report should be completed for any event where doubt exists regarding its status of seriousness.

If the investigator believes that an SAE is not related to the study drug but is potentially related to the conditions of the study (such as a withdrawal of previous therapy or a complication related to study procedure), the relationship should be specified in the narrative section of the SAE Report Form.

All SAEs, whether considered related or not related to study drug, overdose, potential drug induced liver injury (DILI), or pregnancy, must be reported within 24 hours of the investigator becoming aware of the event. The investigator is responsible for submitting all applicable events to the IRB/REB as per the reporting requirements. Additionally, the investigator, or designated staff, is responsible for entering the SAE information into the eCRF with event term, start/stop dates, causality, and severity.

For this study, SAEs will be captured through electronic data capture (EDC) and on the SAE report form. Any SAE must be reported immediately (or no later than 24 hours after awareness of the event) to Pharmaceutical Product Development (PPD) Pharmacovigilance (PVG) using the SAE report form and transmitted by facsimile (fax), which is the preferred method of submission:

- North America – [name]

If a form is unable to be submitted within 24 hours, the SAE may be reported by telephone via the Safety Hotline Number:

- North America – [name]

If only limited information is initially available, follow-up reports are required. If an ongoing SAE changes in its intensity or relationship to study drug or if new information becomes available, a follow-up SAE report should be sent within 24 hours of the investigator becoming aware of the updated information using the same procedure used for the transmission of the initial SAE and the same event term should be used.

The minimum information required for an initial SAE report is:

- Sender of report (site number, investigator name)
- Subject identification (subject number)
- Protocol number (BHV-3500-204)
- SAE term (if an SAE is being reported)

12.2.3 Pregnancy

Following the baseline visit or at any time during the study it is discovered that a subject is pregnant or may have been pregnant at the time of the study drug exposure, including during at least 6 half-lives after study drug administration, the study drug will be permanently discontinued in an appropriate manner (i.e., dose tapering, if necessary, for subject safety).

Protocol-required procedures for study discontinuation and follow-up must be performed by the subject (i.e., follow-up procedures per [Table 10-1](#)).

12.2.3.1 Reporting of Pregnancy

Sites should instruct patients to contact the investigator if they become pregnant during the course of the study. The investigator must immediately notify the Biohaven Medical Monitor (or designee) of the event and complete the Pregnancy Report Form in accordance with SAE reporting procedures as described in [Section 12.2.2](#). The pregnancy should be reported using paper forms, which should be faxed to PPD PVG, which is the preferred method of submission, within 24 hours after investigator/site awareness of the event:

North America – [name]

In the event the Pregnancy Report Form cannot be faxed or emailed, it must be reported via phone to the PPD Safety Hotline at:

North America – [name]

Once the paper form is available, the data must be reported per standard procedures.

Follow-up information regarding the course of the pregnancy, including perinatal and neonatal outcome and, where applicable, offspring information must also be reported on a Pregnancy Report Form.

Any pregnancy that occurs in a female partner of a male study participant should be reported to the Sponsor (or designee), and information on the pregnancy will be collected on the Pregnancy Report Form, as appropriate.

12.2.4 Overdose

An overdose is defined as the accidental or intentional administration of any dose of a product that is considered both excessive and medically important.

All occurrences of medically significant overdose (suspected or confirmed and irrespective of whether it involved zavege pant BHV-3500) must be communicated to Biohaven or a specified designee within 24 hours and be fully documented as an SAE. Details of any signs or symptoms and their management should be recorded including details of any treatments administered.

Asymptomatic dosing errors (e.g., accidentally taking > 12 capsules instead of prescribed dose of 12 capsules in one calendar day) should be reported as a protocol deviation.

12.2.5 Potential Drug Induced Liver Injury

Wherever possible, timely confirmation of the initial liver-related laboratory abnormalities should occur prior to the reporting of a potential DILI event. All occurrence of potential DILIs, meeting the defined criteria, must be reported as SAEs as per [Section 12.2.2](#).

Potential DILI is defined as:

1. ALT or AST elevation $> 3 \times$ the ULN

AND

2. Total bilirubin $> 2 \times$ the ULN, without initial findings of cholestasis (elevated serum alkaline phosphatase)

AND

3. No other immediately apparent possible causes of ALT or AST elevation and hyperbilirubinemia, including but not limited to, viral hepatitis, pre-existing chronic or acute liver disease, or the administration of other drug(s) known to be hepatotoxic.

If any potential DILI is identified and meets the criteria above, the Biohaven Medical Monitor (or designee) should immediately be contacted for further instruction and decision of whether the subject must be discontinued from the trial and appropriate follow-up requirements.

12.3 Demographics and Medical History

Subject demographics will be recorded at screening and include date of birth (or age according to applicable regulations), sex, race, and ethnicity.

Medical history will also be recorded at screening. Investigators should document the occurrence, signs, and symptoms of the subject's pre-existing conditions, including all prior

significant illnesses, up to and including 5 years before screening. Additional pre-existing conditions present at the time when informed consent is given and up to the time of first dosing (Visit 5) are to be regarded as concomitant. Medical history will include alcohol consumption and smoking history, if applicable.

Illnesses first occurring or detected during the study and/or worsening of a concomitant illness during the study are to be documented as AEs on the eCRF in accordance with [Section 12](#). All changes not present at baseline or described in the past medical history and identified as clinically noteworthy must be recorded as AEs.

12.4 Vital Signs

Vital signs (body temperature, respiratory rate, heart rate, and systolic and diastolic blood pressure measurements) will be evaluated at the visits indicated in the Schedule of Assessments ([Table 10-1](#)). All vital signs will be measured after the subject has been resting in a sitting position for at least 10 minutes. Blood pressure measurements are to be taken in the same arm for the duration of the study.

Vital sign measurements will be repeated if clinically significant or machine/equipment errors occur. Out-of-range blood pressure, respiratory rate, or heart rate measurements determined by investigator judgment will be repeated at the investigator's discretion. Any confirmed, clinically significant vital sign measurements must be recorded as AEs.

12.5 Physical Examination

A complete physical examination (head, eyes, ears, nose and throat; heart; lungs; abdomen; skin; cervical and axillary lymph nodes; and neurological and musculoskeletal systems) will be performed at the visits indicated in the Schedule of Assessments ([Table 10-1](#)).

Body weight (without shoes) will be recorded whenever physical examinations are recorded; height (without shoes) will be recorded and BMI will be calculated by the site at screening (Visit 1) only. All physical examinations will be performed by a physician.

Symptom-driven, limited physical examinations will be performed as clinically indicated at any study visit.

12.6 Electrocardiograms

A 12-lead, resting ECG will be measured in triplicate after the subject has rested in a supine or semi-recumbent position for 5 minutes or more at screening and at subsequent visits per Schedule of Assessments ([Table 10-1](#)). The ECG will be performed before spirometry.

At screening, the investigator will examine the ECG traces for signs of cardiac disease that could exclude the subject from the study. An assessment of normal or abnormal will be recorded; if the ECG is considered abnormal, the abnormality will be documented in the eCRF. Investigator

assessment of the abnormality will also be documented in the eCRF. Electrocardiograms will be repeated if clinically significant abnormalities are observed or artifacts are present.

12.7 Spirometry

Spirometry will be measured at time points in the Schedule of Assessments ([Table 10-1](#)), and after a physical examination and an ECG has been performed. Further, spirometry is used to monitor baseline lung function (safety and eligibility) and gauge level of bronchoconstriction during methacholine and allergen challenges.

12.8 Sheehan-Suicidality Tracking Scale

The S-STS is a prospective, clinician-administered rating questionnaire that tracks both treatment-emergent suicidal ideation and behaviors. The S-STS will be performed as outlined in [Table 10-1](#).

This scale will be clinician-administered by a trained rater, completed onsite, and will be in paper format. The source document will be provided by the Sponsor. At the screening visit, the recall period for completing the S-STS will be the last 30 days prior; at all other visits, the recall period for completing the S-STS will be since the subject's last visit.

Subjects who have an S-STS score of > 0 should be evaluated by the investigator. If the investigator determines that a subject is at risk of suicide or self-harm, appropriate measures to ensure the subject's safety must be made and mental health evaluation must be implemented. In such circumstances, the subject must immediately be discontinued from the study. The event should be recorded as determined by the investigator and reported within 24 hours to the Sponsor.

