Washout period: A rest/washout period of 2 to 4 weeks to confirm subject lung function and airway responsiveness to methacholine has recovered (e.g., return of FEV₁ to within 90% of baseline and methacholine PC₂₀ not more than 1 doubling dose lower than baseline). If more than 4 weeks is required, Sponsor Medical Monitor should be consulted.

Part 2 (Dosing period): Duration of study treatment in Part 2 will be approximately 28 days.

At Visit 5/Day 1 (predose), a methacholine challenge will be performed. To continue to randomization, the subject's baseline lung function (FEV₁) and airway responsiveness to methacholine must show evidence of recovery to within 90% of baseline for FEV₁ and not more

than 1 doubling dose below Visit 2 baseline for methacholine PC₂₀. If these criteria are met, sputum will be induced. If subjects have not recovered from the screening allergen challenge, additional time will be allowed, and Visit 5 pre-dosing procedures may be repeated. If additional retest is required, the screening period may be extended beyond 4 weeks.

[figure not shown]
Subjects will then be randomized in a 1:1 ratio to receive 150 mg zavegeptan or matching placebo to be taken BID. Subjects will take their first dose of zavegeptan on a fasted stomach upon waking, and their second dose in the evening. Subjects should not consume food other than water for 1 hour after dosing.

All subjects will be scheduled for their 3-day allergen challenge triad (Visit 6/~Day 26, Visit 7/~Day 27, and Visit 8/~Day 28). Morning doses will be taken before any laboratory procedures. Study treatment will end with the subject's evening dose at Visit 8 (~Day 28). A follow-up period consisting of an onsite visit (Visit 9) will be conducted approximately 7 to 10 days after the last study treatment.

Additional dosing/fasting details are provided in [Section 9.3](#).

[Figure 1](#) presents the general study schematic.

Figure 1. Study Schematic

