- Verification that subject is completing their Meal and Daily Study Drug Dosing Diary.

Visit 7: Onsite (allergen challenge)

- Subjects will be asked to provide the time of their evening dose and meal on evening before this visit.
- After having fasted overnight; a blood sample for PK measurement will be collected for zavegeptan concentration measurement (predose).
- Subjects will take the morning dose onsite at the clinic and should not consume food other than water for 1 hour after dose. Study procedures may begin immediately after dosing.
- Allergen inhalation challenge will be conducted postdose in the morning; spirometry will be measured until 7 hours, and sputum will be induced 7 hours post-allergen challenge.
- Additional blood samples to measure zavegeptan concentrations will be collected at approximately 1 (+ 0.5h) hour and 3 (+/- 0.5h) hours postdose. Exact times of dosing and PK sample collection will be documented.
- Vital signs and spirometry will be recorded.
- AEs, concomitant medications, and ongoing medications will be recorded.
- Verification that subject is completing their Meal and Daily Study Drug Dosing Diary.

Visit 8: Onsite (post-allergen)

- Subjects will be asked to provide the time of their evening dose and meal on evening before this visit.
- After having fasted overnight; a blood sample for PK measurement will be collected for zavegeptan concentration measurement (predose). Subjects will take the morning dose onsite at the clinic and should not consume food other than water for 1 hour. Exact times of dosing and PK sample collection will be documented.
- Vital signs will be measured.
- Spirometry measurements will be performed.
- Pregnancy test conducted for WOCBP.
- Hematology, chemistry, and urine samples will be obtained.
- AEs, concomitant medications, and ongoing medications will be recorded.
- A methacholine challenge will be performed postdose in the morning (24 hours [\pm 3 hours] after the Visit 7 allergen challenge); sputum will be induced.
- Final S-STS will be conducted.
- Verification and collection of Meal and Daily Study Drug Dosing Diary.

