10.2.4 Unscheduled Visit

The investigator may, at his/her discretion, arrange for a subject to have an unscheduled assessment, especially in the case of AEs that require follow-up or are considered by the investigator to be possibly related to the use of study drug. The unscheduled visit page in the eCRF must be completed.

Study discontinuation procedures are described in [Section 8.6](#).

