12 SAFETY ASSESSMENTS

12.1 Adverse Events

An AE is defined as any new untoward medical occurrence or worsening of a pre-existing medical condition in a subject or clinical investigation subject administered an investigational (medicinal) product and that does not necessarily have a causal relationship with this treatment. An AE can therefore be any unfavorable and unintended sign (including an abnormal laboratory finding for example) symptom, or disease temporally associated with the use of the IP, whether or not considered related to the IP.

AEs can be spontaneously reported or elicited during an open-ended questioning, examination, or evaluation of a subject. In order to prevent reporting bias, subjects should not be questioned regarding the specific occurrence of one or more AEs.

If a specific diagnosis or syndrome is identified by the investigator, this should be recorded as the AE, rather than recording (as separate AEs) the individual signs/symptoms or clinically significant laboratory abnormalities known to be associated with, and considered by the investigator to be a component of, the disease/syndrome.

The collection of non-serious AE information should begin from the time of informed consent through the follow-up period (7 to 10 days after last visit). Non-serious AE information should also be collected from the start of a placebo lead-in phase or other observation period intended to establish a baseline status for a subject.

Unchanged, chronic conditions, or those related to the underlying disease or medical conditions that are consistent with natural disease progression are not considered AEs and should not be recorded on AE pages of the eCRF unless there is an exacerbation of a chronic condition.

Definition of terms related to all Adverse Events (both serious and non-serious):

Mild: Is usually transient and may require only minimal treatment or therapeutic intervention. The event does not generally interfere with usual activities of daily living.

Moderate: Is usually alleviated with additional specific therapeutic intervention. The event interferes with usual activities of daily living, causing discomfort but poses no significant or permanent risk of harm to the subject.

Severe: Interrupts usual activities of daily living, significantly affects clinical status, or may require intensive therapeutic intervention.

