10.5. S-STS

The S-STS is a prospective, clinician-administered rating questionnaire with 16 patient-reported questions and 6 clinician-reported questions that tracks both treatment-emergent suicidal ideation and behaviors. The S-STS will be performed at Visit 1, Visit 5, and Visit 8.

Refer to the Core SAP for calculation of the S-STS ideation subscale, behavior subscale, and total scores.

Values and changes from baseline in the self-reported S-STS ideation subscale, behavior subscale, and total score are tabulated descriptively as continuous variables at baseline and the worst (highest) score in the analysis periods. The table also presents the number and percentage of subjects in the worst (highest) score change from baseline category (i.e., < -1, -1, no change, 1, >1) in analysis periods for the ideation subscale, behavior subscale, and total score.

Results are tabulated on-treatment for the safety analysis set.

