11.2. Analysis Periods

Analysis periods are defined as follows:

- Pre-treatment: measurement date/time on or before the study drug start date. This period is used to derive baseline values and to assess safety endpoints. Note that all measurements are pre-treatment for subjects in the enrolled analysis set with missing study drug start date. Note that AEs with imputed start date equal to the study drug start date are NOT part of this period.
 - Pre-treatment will include Visits 1 – 5 / Study Days -29 – 1
- On-treatment: measurement date/time after the study drug start date through the study drug last date + 7 days or ending at the follow-up visit, whichever is earliest. This period is used to assess safety endpoints on treatment. Note that AEs with imputed start date equal to the study drug start date are part of this period.

This document is confidential.

- On-treatment will include Visits 6 – 8 / Study Days 1 – 28
- Follow-up: measurement date after the study drug last date + 7 days or starting at the follow-up visit, whichever is earliest. This period is used to assess safety endpoints during follow-up.
 - Follow-up will include Visit 9 / Study Days 35 – 41

See [Section 11.1](#) for derived dates for determining analysis periods. If measurement time is missing, not collected, or not applicable for a parameter, then the measurement date is compared to the derived date.

This document is confidential.

12. Interim Analyses

No interim analyses are planned for this study.

This document is confidential.

SAP text Version: SAP text version 2.0 24-May-2023

Filing requirements: TMF

Page 36 of 42

13. Changes from Analysis Planned in Protocol

The Treated Population is defined in the study protocol. However, it has been renamed the Safety Population in the SAP.

One additional study populations were added that are not defined in the study protocol, the Follow-up population.

This document is confidential.

14. Quality Control

SAS programs are developed to produce output such as analysis data sets, summary tables, data listings, figures or statistical analyses. An overview of the development of programs is detailed in Syneos Health Developing Statistical Programs SOP (3907) .

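### The S-STS recall rule in Protocol 12.8 runs from the subject's last visit, not the last S-STS, so read as written the only scheduled post-dose rating covers about 1 of 27 nominal days

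*Protocol*

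**What the plan says.** Protocol 12.8 describes the S-STS as a clinician-administered scale that tracks treatment-emergent suicidal ideation and behaviors. A trained rater completes it on a paper form supplied by the Sponsor. Recall at screening is the preceding 30 days. After that, "at all other visits, the recall period for completing the S-STS will be since the subject's last visit". A score above 0 calls for evaluation by the investigator.

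The schedule is consistent across both documents. SAP 10.5 states: "The S-STS will be performed at Visit 1, Visit 5, and Visit 8". The S-STS rows of Protocol Table 10-1 and SAP Table 2 agree. In Protocol 10.2.2 the Visit 5 rating is among the predose assessments, and the Visit 8 list reads "Final S-STS will be conducted". Visit 9 has none.

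Visit 8 closes a run of three consecutive visits. Protocol 7.1 says "All subjects will be scheduled for their 3-day allergen challenge triad" and places Visits 6, 7 and 8 at about Days 26, 27 and 28. Protocol 10.2.2 lists Visits 6 and 7 as onsite visits, without an S-STS at either. Visits 2 to 4 likewise fall between the Visit 1 and Visit 5 ratings.

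For analysis, SAP 10.5 tabulates the worst score and its change from baseline, and says: "Results are tabulated on-treatment for the safety analysis set". It mentions no recall window and refers to the Core SAP for score calculation.

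**The concern.** A recall rule tied to the previous visit works when the scale is given at every visit. Here it is not. Visit 8 comes one day after an onsite visit with no S-STS, so the words as they stand shorten the look-back to about a day. Ideation or behavior between Visit 5 and Visit 7 would then not enter the Visit 8 score, would not trigger the evaluation tied to a score above 0, and could not be recovered by any later scheduled S-STS. That sits badly with a scale whose stated purpose is to track treatment-emergent events.

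The table in SAP 10.5 is affected as well. With no window stated, a zero at Visit 8 could describe one day or the whole dosing period. Baseline under SAP 6.2 is the last value before first dose, nominally Visit 5, and the same wording shortens that rating's recall too. Change from baseline would then compare two windows of different length. With about 6 sites and trained raters working from written instructions, different raters could also apply the rule differently within one table.

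**Working it through.** The documents give no recall length in days after screening, so there is no stated figure to reproduce. The check is day subtraction on the nominal schedule. SAP 6.2 has no Day 0, so Day -a to Day 1 is a days.

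**Inputs**
- Visit 1: Day -29 to Day -16; Visit 4: Day -13 (Protocol Table 10-1)
- Visit 5: Day 1, predose (Protocol 10.2.2)
- Visits 7 and 8: about Days 27 and 28, each with a +3 day window (Protocol 7.1, Table 10-1)
- Visit 8 methacholine challenge: 24 ± 3 hours after the Visit 7 allergen challenge (Protocol 10.2.2)

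**Visit 8 rating**
- Interval since the previous S-STS (Visit 5): 28 − 1 = 27 days
- Recall as written (since Visit 7): 28 − 27 = 1 day
- Outside recall: 27 − 1 = 26 days; 26/27 = 96%
- With the triad 3 days late (Visit 7 on Day 30, Visit 8 on Day 31): 31 − 1 = 30 days; 30 − 1 = 29 outside; 29/30 = 97%
- Taking the 24 ± 3 hour spacing as the visit spacing: 21/24 = 0.875 to 27/24 = 1.125 days of recall, so 27 − 1.125 = 25.9 to 27 − 0.875 = 26.1 days outside

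**Visit 5 rating**
- Interval since the previous S-STS (Visit 1): 16 to 29 days
- Recall as written (since Visit 4): 13 days
- Outside recall: 16 − 13 = 3 to 29 − 13 = 16 days

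| Rating | Days since previous S-STS | Covered as written | Covered if last visit means last S-STS visit |
|---|---|---|---|
| Visit 5 | 16 to 29 | 13 | 16 to 29 |
| Visit 8 | 27 | 1 | 27 |

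These are nominal days. Visit windows and a washout of up to 4 weeks or more lengthen or shift some intervals, but they do not change the pattern.

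**The case against.** The strongest reply is that the literal reading is strained. In the same sentence of 12.8, the phrase about all other visits can only mean visits at which the S-STS is given, so the last visit is naturally read the same way. A literal rule would also impair both post-screening uses of the scale, which makes it unlikely to be what the authors meant. On the contextual reading no day is missed. This stands as an argument about intent. It does not put the rule into the text that raters follow.

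Second, sources not available here may settle the matter. The Sponsor's paper form may print the window, and the Core SAP takes primacy where this SAP is silent. That also stands: the finding is about the protocol and this SAP only.

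Third, there are other safeguards. AEs are recorded at Visits 6 to 9, SAEs are collected from consent, and under Protocol 10.2.4 the investigator may "arrange for a subject to have an unscheduled assessment". SAP 10.1.2 and 10.6 carry suicidality AEs into the overview and the narrative listing. Entry requires a screening S-STS score of 0, and there are psychiatric exclusions. The backstop remains partial. Protocol 12.1 allows open-ended questioning but says "subjects should not be questioned regarding the specific occurrence of one or more AEs", so it does not replace a structured rating.

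A reader might also measure the gap against the on-treatment period in SAP 11.2, which runs "after the study drug start date through the study drug last date + 7 days" or to the follow-up visit, if earlier. The documents do not support charging the days after Visit 8 to the recall wording. They are uncovered because Visit 9 has no S-STS, a separate scheduling choice that rewording would not alter.

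**Conclusion.** The point holds as an ambiguity in a stated rule. As written, the only scheduled post-dose S-STS covers about 1 of 27 nominal days, and the Visit 5 rating leaves 3 to 16 nominal days between Visits 1 and 4 unrated. If the last visit means the last S-STS visit, coverage is complete. Neither document says which applies.

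A reader might infer that suicidality went unassessed for nearly all of dosing. The documents do not show that. They do not show which window raters used, the contextual reading is plausible, and AE and SAE collection ran throughout. Nor is this a contradiction between sections: the S-STS schedule is the same everywhere.

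The consequence is minor and confined to safety monitoring. The S-STS is not among the measures named in the secondary safety endpoint (Protocol 6.2.2), and no efficacy conclusion depends on it. Confidence is medium. It rests on nominal visit days and on the Sponsor's form and the Core SAP being unavailable.

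**What to change.** In Protocol 12.8 and the rater instructions, define post-screening recall as running from the last S-STS assessment instead of the last visit. This corrects Visits 5 and 8 together, costs one phrase, and adds no assessment.

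SAP section 2 records that the study was terminated in 1Q2023, so rewording cannot change data already collected. For those data, check the S-STS source forms and rater instructions. If they show the window used, state it in a footnote to the SAP 10.5 table. If they do not, the footnote should say that the Visit 8 window is uncertain, between about 1 and 27 days, and refer the reader to the suicidality-AE summaries. This costs one document check and one footnote, with no reanalysis.
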